# List of Abbreviations

**CDT:** Complete decongestive therapy

HNC: Head and neck cancer

LLLT: Low-level laser therapy

CONFIDENTIAL

This material is the property of the University of Pennsylvania.

# **Study Summary**

Title	Low-Level Laser in Treatment of Head and Neck Chronic Lymphedema: A Pilot Randomized Controlled Trial
Short Title	Low-level laser therapy in head and neck chronic lymphedema
Study ID Number	UPCC01320
Protocol Number	Version Date: 09-12-2022
Phase	Pilot study
Methodology	Randomized, wait-list controlled trial
Study Duration	24 months
Study Center(s)	Single-center
Objectives	Primary Aim : To determine the impact of LLLT, as compared to a wait-list control, on changes in severity of lymphedema. Secondary Aim : To determine the impact of LLLT, as compared to a wait-list control, on lymphedema-related symptom burden (e.g., tightness), functional impairments (e.g., range of motion in the jaw and neck) and QOL. Exploratory Aim : To explore the relationships among LLLT, the inflammatory biomarkers (e.g., TNF-α, TGF-β, IL-6), and the severity of lymphedema.
Number of Subjects	40 subjects expected to be enrolled
Main Inclusion and Exclusion Criteria	Inclusion criteria: 1) >18 years of age; 2) > 6 months post HNC treatment; 3) no evidence of cancer confirmed with imaging tests within 6 months or clinical examination by an oncologist as documented by progress note; 4) having head and neck lymphedema with or without fibrosis; 5) completion of initial lymphedema therapy; 6) lymphedema duration between 3-36 months; 7) ability to speak and read English; and 8) ability to provide informed consent. Exclusion criteria : Patients will be excluded if they have any of the following medical conditions that would prohibit the safe implementation of LLLT: pregnancy; acute infection; photosensitivity; chronic inflammatory diseases; venous thrombosis; carotid artery stenosis; history of severe trauma; medication that affects body fluid and electrolyte balance; use of high doses of non-steroidal anti-inflammatory drugs; or pre-existing skin rash, ulceration, open wound in the treatment area; active lymphedema therapy or physical therapy; and allergic and other systemic skin diseases.
Investigational device For Device include the planned use	RianCorp LTU-904 Low-level laser therapy unit
Duration of administration (if applicable)	6 weeks
Reference therapy	Usual care – Wait-list control
Safety Evaluations	Common Terminology Criteria for Adverse Events (CTCAE version 5.0) will be used to document adverse events of the clinical trial.
Data and Safety Monitoring Plan	PI [name] will be responsible for monitoring the data quality and the ongoing safety of subjects. The Medical Monitor, [name], will monitor and review all AEs and other safety data and activity data observed in the trial.

This study will be conducted in full accordance with all applicable University of Pennsylvania Research Policies and Procedures and all applicable Federal and state laws and regulations including the use of a medical device (i.e., RianCorp LTU-904).

### 1 Introduction

Current standard of care for head and neck lymphedema treatment provided by therapists is shortterm in nature (usually up to 4-8 weeks); however, lymphedema is a chronic condition and often worsens over time. Therefore, alternative treatment modalities need to be investigated for effective and long-term management of lymphedema and associated late fibrosis in the head and neck cancer (HNC) population.

### 1.1 Background and Relevant Literature

There has been an increase in the incidence of head and neck cancer (HNC) largely related to the epidemic of human papillomavirus (HPV) associated disease. HPV- associated HNC occurs in younger and middle-aged patients; cure rates in this population are markedly higher compared to other HNC groups. This contributes to more than half a million HNC survivors in the U.S. today. Regardless of the cause, patients with locally advanced HNC are usually treated with aggressive multi-modality regimens. These regimens often lead to numerous long-term toxicities. One common but under-treated late effect of treatment is damage to lymphatic structures and soft tissues resulting in lymphedema. Animal studies indicate that lymphedema is associated with chronic inflammation leading to fibrosis.9,10 Our work was the first to assess lymphedema in HNC patients in a systematic manner. We demonstrated a prevalence rate of 75% in HNC survivors. We confirmed that lymphedema occurs both externally (e.g., face and neck) and internally (e.g., pharynx and larynx). Subsequent work demonstrated that external lymphedema resulted in a decreased range of motion in the jaw, neck, and shoulders. Internal swelling was found to cause substantial impact on critical functions (e.g., swallowing, speaking, and breathing). Psychological effects (e.g., body image disturbance) were also correlated with lymphedema. Finally, lymphedema has the potential to negatively impact HNC survivors' ability to function in both home and work environments, resulting in both emotional and financial burden for these individuals, their families, and the healthcare system.

The current standard of care for treatment of lymphedema is complete decongestive therapy (CDT), which consists of 4 main parts: manual lymphatic drainage, compression (bandaging or garments), exercise, and skin care.  These treatments are expensive, time-consuming, and labor-intensive. Although CDT is routinely used in clinical settings, no level I evidence is available on the use of CDT for the treatment of HNC-related lymphedema. In addition, CDT provided by therapists is short-term in nature (usually up to 4-12 weeks); however, lymphedema is a chronic condition and often worsens over time. Therefore, alternative treatment modalities need to be investigated for effective and long-term management of lymphedema and associated late fibrosis in the HNC population.

Among many alternative treatment options, low-level laser therapy (LLLT) is a promising, noninvasive modality for the treatment of lymphedema. LLLT, also named photobiomodulation therapy (PBMT), has had a place in general medicine for more than 40 years. It has been used as a treatment option to stimulate wound healing and reduce inflammation, edema, and pain. The U.S. Food and Drug Administration (FDA) accepted it as a treatment approach for breast cancer-related upper extremity lymphedema (BCRL) in 2006. One recent systematic review evaluating 7 randomized clinical trials (RCT) concluded that available evidence supports LLLT in the management of BCRL, with clinically meaningful reductions in lymphedema-related swelling and symptom burden (e.g., pain). Compared to other treatment modalities, LLLT is a noninvasive modality, repeatable, easily performed in outpatient settings, and without any known long-term side effects. LLLT may be effective in treating chronic lymphedema in the HNC population, as it may reduce the generation of proinflammatory cytokines (e.g., tumor necrosis factor-alpha, TNF- $\alpha$ ) and increase anti-inflammatory cytokines (e.g., interleukin-10, IL-10). This is particularly important because many HNC survivors develop both lymphedema and late fibrosis.

Low-Level Laser Therapy in Head and Neck Chronic Lymphedema Version: 9-12-2022

Therefore, LLLT may have the potential to effectively treat and manage HNC-related lymphedema. To our knowledge, the current proposal is the first RCT investigating the use of LLLT in the treatment of head and neck chronic lymphedema. The goal of this study is to evaluate the effect of LLLT on the severity of lymphedema, symptom burden, functional status, and quality of life (QOL) in HNC survivors, through a pilot, randomized, wait-list controlled trial.

### 1.2 Name and Description of the Investigational Product

We will use a RianCorp LTU-904, FDA-approved, Class I laser device in this study. The device will be used by the study lymphedema therapist, [name], who has had more than 20 years of experience treating individuals with lymphedema.

# 1.2.1 Nonclinical Data

Findings from nonclinical data indicate that LLLT stimulates lymphatic vessels and lymphocytes, as well as increases local fluid circulation.

### 1.2.2 Clinical Data to Date

Currently, only case studies indicate the potential value of the use of LLLT for treating head and neck lymphedema. No prospective trials are available to evaluate feasibility, prophylactic and/or therapeutic use of LLLT for lymphedema in HNC patients. However, a large body of evidence is available in supporting the safety and efficacy of LLLT for the management of lymphedema in breast cancer patients. For instance, since 1995, the use of LLLT has been investigated in the treatment of breast cancer-related lymphedema (BCRL). A meta-analysis of 9 studies (7 of them were RCTs) provided evidence that LLLT alone or combined with other treatments was able to reduce the arm swelling and pain in women with BCRL. LLLT does not increase the risk of cellulitis, a known side effect in patients with arm lymphedema. A recent systematic review also suggested the use of LLLT for treating the following conditions in the breast cancer population: oral mucositis, radiodermatitis, chemotherapy-induced peripheral neuropathy, and osteonecrosis of the jaw. In another recent systematic review, the authors concluded that LLLT may have potential applications in the management of a broad range of side effects (e.g., lymphedema/fibrosis) of chemo-radiation therapy in patients with HNC.

To fill in the gap, we have recently completed a **pilot**, **single-group**, **pre-post design clinical trial**, **the first prospective trial in this area**, that demonstrated it is feasible and acceptable to use LLLT for treating chronic lymphedema in HNC survivors.

### 1.2.3 Clinical Studies in Children

Not applicable.

# 1.3 Dose Rationale (if applicable)

We propose that participants will receive LLLT twice a week for 6 weeks (12 sessions). This regimen was developed based on the evidence from the literature as well as the data from our pilot feasibility trial.

# 2 Study Objectives

The major objective of this proposed research is to determine preliminary efficacy of the use of LLLT for HNC survivors with chronic lymphedema.

### 2.1 Primary Objective

• To determine the impact of LLLT, as compared to a wait-list control, on changes in severity of lymphedema.

Low-Level Laser Therapy in Head and Neck Chronic Lymphedema Version: 9-12-2022

### 2.2 Secondary Objective

• To determine the impact of LLLT, as compared to a wait-list control, on lymphedema-related symptom burden (e.g., tightness), functional impairments (e.g., range of motion in the jaw and neck) and QOL.

### 2.3 Exploratory Objective

• To explore the relationships among LLLT, the inflammatory biomarkers (e.g., TNF- $\alpha$ , TGF- $\beta$ , IL-6), and the severity of lymphedema.

### 3 Investigational Plan

# 3.1 General Design

We will conduct a randomized, wait-list controlled trial to compare: Group 1 (laser therapy) and Group 2 (wait-list control). Outcome measures include: 1) changes in severity of lymphedema [Primary aim]; 2) changes in lymphedema-related symptom burden, functional status, and QOL [Secondary aim]; and 3) the relationships among LLLT, the inflammatory biomarkers, and severity of lymphedema [Exploratory aim].

# 3.1.1 Screening Phase

We will recruit a minimum of 3-4 participants per month. The volume of HNC patients at Penn's Clinic is sufficient to complete this trial without additional sites. The following recruitment procedures will be used: screening at HNC clinics and attendance at Head and Neck tumor boards and case conferences. All direct patient recruitment activities will be conducted at the Penn HNC clinics where private rooms are available to be used for conducting clinical research projects.

# 3.1.2 Allocation to Interventional Group

After completion of baseline measures, participants will be randomized via a computer-generated, permuted block program, conducted by Co-I Statistician [name], to one of 2 arms: Group 1 (laser therapy) and Group 2 (wait-list control). Randomization will be stratified by lymphedema laterality (unilateral vs. bilateral) with a 1:1 allocation, which will allow us to balance potentially important subgroups equally among the two groups.

### 3.1.3 Study Intervention Phase and Follow Up Phase

Group 1 (laser group): After completion of the baseline measures, Group 1 participants will be scheduled for LLLT. The LLLT includes receiving LLLT twice a week for 6 weeks (12 sessions). After completion of the 12-sessions of LLLT, participants will be given a) contact information and instructions to call for problems and b) a calendar outlining dates for the 4- and 8-week post-LLLT follow-up data collection. Group 1 participants will need to complete 4 study assessment visits.

Group 2 (wait-list control group): After completion of the baseline measures, Group 2 participants will not undergo the LLLT therapy but will complete all the same study assessments as the laser therapy group, including the baseline, 6-week after the baseline, 10-week and 14-week after the baseline assessments. After the 14-week baseline assessment, they will be offered the same LLLT sessions as the laser group. After completion of the 12-sessions of LLLT, participants will undergo the 4- and 8-week post-laser follow-up data collection. Group 2 participants will need to complete 7 study assessment visits.

# 3.2 Study Endpoints

# 3.2.1 Primary Study Endpoints

The primary endpoint will be the preliminary efficacy of LLLT in HNC survivors, including changes in severity of lymphedema using the Head and Neck Lymphedema and Fibrosis (HN-LEF) Assessment Criteria.

# 3.2.2 Secondary Study Endpoints

The secondary study endpoint will be the impact of LLLT on lymphedema-related symptom burden (e.g., tightness), functional impairments (e.g., range of motion in the jaw and neck), and QOL.

# 4 Study Population and Duration of Participation

### 4.1 Inclusion Criteria

- >18 years of age
- > 6 months post HNC treatment
- No evidence of cancer confirmed with imaging tests within 6 months or clinical examination by an oncologist as documented by progress note
- Having head and neck lymphedema with or without fibrosis
- Completion of initial lymphedema therapy
- Lymphedema duration between 3-36 months
- Ability to speak and read English
- Ability to provide informed consent

### 4.2 Exclusion Criteria

Patients will be excluded if they have any of the following medical conditions that would prohibit the safe implementation of LLLT: pregnancy; acute infection; photosensitivity; chronic inflammatory diseases; venous thrombosis; carotid artery stenosis; history of severe trauma; medication that affects body fluid and electrolyte balance; use of high doses of non-steroidal anti-inflammatory drugs; or pre-existing skin rash, ulceration, open wound in the treatment area; active lymphedema therapy or physical therapy; and allergic and other systemic skin diseases.

### 4.3 Subject Recruitment

The following recruitment procedures will be used: screening at HNC clinics and attendance at Head and Neck tumor boards and case conferences. All direct patient recruitment activities will be conducted at the Penn HNC clinics where private rooms are available to be used for conducting clinical research projects.

### 4.4 Duration of Study Participation

The duration of the study subjects' participation will be 14 weeks (laser group) – 28 weeks (wait-list control group), including screening, study intervention phase (6 weeks) and any follow-up time period.

### 4.5 Total Number of Subjects and Sites

Total number of subjects: 40

Total number of subjects was determined with consideration for an estimated 20% attrition rate. Single-site study: Subjects will be enrolled at Penn only.

### 4.6 Vulnerable Populations

Although not directly targeted, mentally disabled persons, economically or educationally disadvantaged persons, and/or employees or students of the University of Pennsylvania will not be denied enrollment and any special protections and/or additional safeguards will be undertaken in order to protect the rights and welfare of these subjects from coercion or undue influence as appropriate.

# 5 Study Intervention (Study drug, device, biologic, vaccine, food, etc.)

Group 1 participants will be scheduled for LLLT.

Group 2 participants will be scheduled for the LLLT after they complete the baseline visit and 3 follow-up assessment visits.

The RianCorp LTU-904 laser therapy unit will be used for LLLT.

# 5.1 Description

The LTU-904 is a Class I laser device, which is a low output laser in the infrared wavelength (904nm) and no safety glasses are required as there is no risk of eye damage as defined by the standards set by the International Electrotechnical Commission.

# 5.2 Intervention Regimen

The LTU-904 will be used in the study. The following LLLT parameters were successfully tested and finalized through our pilot study will be used in the proposed clinical trial: 904nm wavelength in pulsed mode, 5mW output, spot size of 0.2 cm^2, and dosage (energy density) of 1.5J/cm^2.

Participants in the laser group will undergo the following procedures at each laser therapy visit. First, they will be asked to lie flat on their back on a treatment bed. The study lymphedema therapist will conduct simple manual lymph drainage in the head and neck region. Then, the trained study lymphedema therapist will mark the participant's treatment anatomical sites in the face and neck region, using a skin-safe and washable marker. A total of 12-22 spots on the face and neck will be treated. The spots include: mandible (2 points), pre auricular (1 point), submental (2 points), sternocleidomastoid muscle (3 points), supraclavicular area (2 points), and scalene muscle (2 points). The lymphedema therapist will place the laser device head vertically and lightly touch the treatment spots on the participant's face and neck region. Each spot will be treated for 60 seconds. After the laser therapy, the lymphedema therapist will help clean the patient's marks using a skin-friendly, anti-bacterial wipe. Each laser therapy session will take approximately 20-30 minutes.

Participants in the wait-list control group will undergo the same procedures for the low-level laser therapy after they complete all the study assessment visits.

### 5.3 Receipt

The LTU-904 will be purchased from RianCorp directly. The device will be shipped to the PI directly.

### 5.4 Storage

The LTU-904 unit comes with a carrying case that ensures the unit is stored safely. Both the PI [name] and the study lymphedema therapist ([name]) were trained by an expert from RianCorp directly regarding how to store, dispense, and manage the device appropriately in PI [name]'s previous pilot feasibility study. The study lymphedema therapist will be responsible for storing, dispensing, and managing the laser device. The study lymphedema therapist will evaluate and monitor the LTU-904 unit regularly to ensure its normal function and prepare it for administration to subjects. The study lymphedema therapist will make sure the LTU-904 is stored properly after use of the device each time. The study lymphedema therapist will report the failed device to the PI [name]. The PI [name] will return the failed device to the manufacturer. The PI [name] will monitor the storage, delivery, management, and use of the laser device throughout the study.

### 5.5 Preparation and Packaging

The study lymphedema therapist will properly prepare the LTU-904 unit for administration to subjects. The study lymphedema therapist will make sure the LTU-904 is stored properly after use of the device each time.

Not applicable.

# 5.7 Subject Compliance Monitoring

The participants are encouraged to be compliant with the scheduled visits. The reasons for non-compliance with the study scheduled visits will be documented and potential underlying barriers will be explored.

# 5.8 Screening

The screening will be conducted by a trained staff member. Individuals who are interested in this research will be screened for eligibility for being in the study. A Screening Checklist will be used to ensure that eligible participants are enrolled in the study. A Recruitment Log will be used during the recruitment.

# 5.9 Baseline Assessment – Visit 1

The following procedures and data collection will take place at study visit 1.

- Demographic Form
- Physical Exam for completing HN-LEF Grading Criteria
- Digital photographs of face and neck
- Modified Patterson Scale
- Symptom burden assessments (HN-LEF Symptom Inventory and NDI)
- Functional status (jaw/neck/shoulder range of motion)
- Quality of life status (EORTC QLQ-H&N35)
- Blood sample (10 cytokines)

In addition, the following variables will be abstracted from the medical chart with participants' permission.

- HNC Disease and treatment information (HNC Clinical Form)
- Lymphedema and fibrosis diagnosis and treatment information (LEF Treatment Form)

# 5.10 Study Intervention Phase – 6- Week Low-Level Laser Therapy

### 5.11 Follow-Up Assessments

# 5.11.1 Visit 2: Follow-Up Assessment (either End of Intervention for Group 1 or 6-week after the baseline for Group 2)

The following procedures and data collection will take place at study visit 2.

- Physical Exam for completing HN-LEF Grading Criteria
- Digital photographs of face and neck
- Symptom burden assessments (HN-LEF Symptom Inventory and NDI)
- Functional status (jaw/neck/shoulder range of motion)
- Quality of life status (EORTC QLQ-H&N35)

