# 5.11.2 Visit 3: Follow-Up Visit (either 4 – week post laser therapy for Group 1 or 10-week after the baseline for Group 2)

The following procedures and data collection will take place at study visit 3.

- Physical Exam for completing HN-LEF Grading Criteria
- Digital photographs of face and neck
- Symptom burden assessments (HN-LEF Symptom Inventory and NDI)
- Functional status (jaw/neck/shoulder range of motion)
- Quality of life status (EORTC QLQ-H&N35)

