# 5.11.3 Visit 4: Follow-Up Visit (either 8 – week post laser therapy for Group 1 or 14-week after the baseline for Group 2)

The following procedures and data collection will take place at study visit 4.

- Physical Exam for completing HN-LEF Grading Criteria
- Digital photographs of face and neck
- Modified Patterson Scale
- Symptom burden assessments (HN-LEF Symptom Inventory and NDI)
- Functional status (jaw/neck/shoulder range of motion)
- Quality of life status (EORTC QLQ-H&N35)
- Blood sample (10 cytokines)

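### Does timing Group 1's Visits 2–4 from the end of laser, and Group 2's from baseline, spoil the comparison of the arms?

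*Combined protocol and SAP*

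**What the plan says.** The two arms count Visits 2 to 4 from different starting points:

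- **Visit 2** (Section 5.11.1): "Visit 2: Follow-Up Assessment (either End of Intervention for Group 1 or 6-week after the baseline for Group 2".
- **Visit 3** (Section 5.11.2): 4 weeks on for Group 1, given as "week post laser therapy for Group 1 or 10-week after the baseline for Group 2".
- **Visit 4** (Section 5.11.3): 8 weeks on for Group 1, given as "week post laser therapy for Group 1 or 14-week after the baseline for Group 2".

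The order of events is baseline, then randomisation, then booking of laser. Section 3.1.2 says "After completion of baseline measures, participants will be randomized via a computer-generated, permuted block program", and Section 3.1.3 says "After completion of the baseline measures, Group 1 participants will be scheduled for LLLT". The course is 12 sessions, two a week for six weeks. Section 3.1.3 continues "After completion of the 12-sessions of LLLT, participants will be given" contact details and a calendar for the two later visits. It also states, without condition, that Group 1 has four assessment visits to complete.

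Section 4.4 puts participation at 14 weeks for the laser group and 28 for the wait-list group, "including screening, study intervention phase (6 weeks) and any follow-up time period". On missed visits, Section 5.7 says only "The reasons for non-compliance with the study scheduled visits will be documented and potential underlying barriers will be explored". Section 6 names mixed effects and GEE models, but does not say whether time enters as visit number or as actual weeks, and does not define the analysis set.

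**The concern.** A wait-list comparison is cleanest when both arms are measured at the same time since randomisation. Here a late start or an extended course moves Group 1's target dates and leaves Group 2's where they are. The Introduction describes lymphedema as chronic and prone to worsen, so later assessment of the laser arm could count against laser. A participant who stopped early and was timed from the last session would be seen sooner than the controls, which could count in laser's favour.

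The second worry is the non-completer. If the later visits are triggered only by finishing all 12 sessions, someone who has fewer has no dates. Outcome collection in one arm would then depend on adherence, and the comparison would drift away from the groups as randomised. The pilot is meant to inform a future trial, so a distorted effect estimate could be carried forward.

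**Working it through.** **1. The plan's own schedule.** Inputs are the 6-week course (Section 3.1.3) and the visit definitions (Sections 5.11.1 to 5.11.6).

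- Group 1: 6 + 0, 6 + 4, 6 + 8 = weeks 6, 10, 14.
- Group 2, control period: weeks 6, 10, 14.
- Group 2, after its own laser: 14 + 6 + 0, 14 + 6 + 4, 14 + 6 + 8 = weeks 20, 24, 28.

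The totals of 14 and 28 weeks reproduce Section 4.4. On plan the arms coincide.

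**2. How far Group 1 could move.** The documents give no start lag and no missed-session rate, so both are assumptions. Twelve sessions half a week apart span 11 × 0.5 = 5.5 weeks. If missed sessions are made up at the end, mean Visit 2 week = mean lag + 5.5 + 0.5 × 12p/(1 − p), where p is the chance of missing a session. The percentages come from simulation with a uniform lag and independent misses.

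| Start lag (weeks) | p | Mean Visit 2 week | Last session after week 6 | Mean sessions received by week 6 |
|---|---|---|---|---|
| 0–1 | 0 | 0.5 + 5.5 = 6.0 | 50% | 11.5 |
| 0–1 | 0.10 | 0.5 + 5.5 + 0.67 = 6.7 | 86% | 10.35 |
| 0.5–2 | 0 | 1.25 + 5.5 = 6.75 | 100% | 10.0 |
| 0.5–2 | 0.20 | 1.25 + 5.5 + 1.5 = 8.25 | 100% | 8.0 |

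If missed sessions are not made up, the last session moves little: mean week 5.9 in the second row and 6.6 in the fourth.

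**3. What the shift would do.** Bias = excess weeks × drift per week. The drift is also assumed, at 0.01 to 0.05 SD per week.

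- Low end: 0.7 × 0.01 = 0.007 SD. High end: 2.25 × 0.05 = 0.1125 SD.
- Section 4.5 allows 20% attrition: 40 × 0.8 = 32, or 16 per arm. The single-visit standard error is √(1/16 + 1/16) = 0.354 SD.
- Bias over standard error: 0.007/0.354 = 0.02 to 0.1125/0.354 = 0.32. Coverage of a 95% interval, Φ(1.96 − r) − Φ(−1.96 − r), runs from 95.0% down to 93.8%.
- In a repeated-measures model over three follow-up visits the standard error is about 0.22 to 0.24 SD, so the worst case is about half of one standard error and coverage is about 92%. That needs the longest lag, 20% missed, every miss made up and the steepest drift together.

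**4. Early stoppers.** Someone who stops after session 6 has the last session at 5 × 0.5 = 2.5 weeks, which is 3.5 weeks ahead of week 6. If two to four of 20 did so and were timed from that session, the Group 1 mean would move by between 3.5 × 0.01 × 2/20 = 0.0035 and 3.5 × 0.05 × 4/20 = 0.035 SD, in laser's favour.

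**5. What the analysis can absorb.** In a simulation with no true effect and linear drift (16 per arm, four visits), modelling visit number gave a shift of 0.005 to 0.118 SD. Modelling actual weeks since baseline brought it within 0.01 SD. The models in Section 6 allow actual time, and nothing there commits the analyst to visit number. The correction is only as good as the assumption of near-linear drift.

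**6. The non-completer, read in context.** The sentence in Section 3.1.3 about finishing 12 sessions says when a calendar is handed over. The same paragraph gives Group 1 four assessment visits with no condition attached. Sections 5.11.2 and 5.11.3 count from laser therapy, not from a twelfth session, and Section 5.10 describes the phase as six weeks long, so the end of intervention can be read as the end of that phase. Sections 5.12 and 8.2 both deal with remaining in or leaving the study and do not conflict.

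**The case for a change.** The best argument for acting is that the match between the arms is fragile and the repair is only wording. Laser is booked after baseline and randomisation, with half a week of slack at most, and the 14 weeks in Section 4.4 leave no room for lag. The plan does not say from which date an early stopper is followed: counted from a last session at week 2.5 the visits fall at weeks 2.5, 6.5 and 10.5; counted from baseline they fall at 6, 10 and 14. That choice is better made before the data are seen.

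The factual part stands. The anchors differ, no window is stated, and a late start moves only Group 1's target dates. Reading the end of intervention as the end of the planned six weeks reduces the effect of missed sessions but does not remove a start lag.

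The step from there to a needed change is weaker. With no window in either arm, Group 2 visits can also be held late, so the one-sided shift applies to target dates and not necessarily to actual ones. The end-of-course anchor is a legitimate choice, since it holds time since treatment constant. Moving to fixed weeks gives that up, and does so most where delays are largest: at week 6 the fourth row of the table has only 8.0 of 12 sessions delivered on average. Keeping the anchor and adding a window, a lag and a time variable would only record what a competent analyst would settle anyway.

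**Conclusion.** The concern does not call for a change. The plan's stated schedule gives the same assessment weeks in both arms and agrees with its own duration figures. The different anchors are a fair trade-off between equal time since baseline and equal time since treatment. The missing details are ones that study staff and analysts can be expected to fill sensibly: following Group 1 participants for their four visits, keeping them in their assigned arm, and checking results against actual weeks. This assumes that visit dates are recorded, as is routine.

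Under assumed delays and drift, the bias from late visits is about 0.01 to 0.11 SD against laser, and from early stoppers 0.004 to 0.035 SD in its favour. The net size and direction cannot be found from the documents and are probably small beside a single-visit standard error of 0.35 SD. The conclusion would weaken if delays were long and common, or if severity changed quickly over a few weeks. The documents give no figure pointing to either.
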